1) **Title:** A Phase 2 trial of Neurokinin-1 Receptor Antagonist for the Treatment of Itch in Epidermolysis Bullosa patients

2) **PI:** [name], PhD

3) **Funding:** Epidermolysis Bullosa Research Partnership (SPO # 117763)

4) **Fund sources for this project:**

Epidermolysis Bullosa Research Partnership (EBRP) – provided funding
Menlo Therapeutics, Inc. – provided study medication

5) **Specific aims:**

This study aims to determine the safety profile of Serlopiant (or VPD-737) in children (>13 y.o.) and adults with pruritus associated with epidermolysis bullosa (EB). This study also aims to determine the efficacy of Serlopiant (5 mg) compared with placebo on reducing EB itch as measured by patient self-reports using a numeric rating scale (NRS) for itch severity and the Stanford EB itch questionnaire. A secondary aim of this study is to determine whether Serlopiant when compared with placebo reduces EB wounds and promotes healing as determined by serial photographs.

It is our hope that Serlopiant will reduce itch in adolescents and adults with EB.

6) **General background:**

NK1 receptor antagonists (Aprepitant and Serlopiant) were originally tested in clinical trials as an antiemetic and a medication to treat overactive bladder. Since 2005, NK1 receptor antagonists have been evaluated in 13 completed Phase I studies and two Phase 2b studies (N=300 subjects). Serlopiant has been well tolerated in young men at a single dose of 400mg, and in the elderly at a dose of up to 20mg. Repeat dosing of up to 50 mg a day for 4 weeks was well tolerated in young adults and elderly males. There were no drug-related serious adverse events (SAE) in these Phase I studies.

In a double-blinded, 6-week randomized trial of 257 adults with chronic pruritus, Serlopiant was shown to decrease itching significantly in a dose-dependent manner (submitted NEJM, clinicaltrials.gov NCT01951274). Participants in this study had chronic pruritus due to a variety of dermatologic, neuropathic, and psychogenic causes that was unresponsive to topical steroids and antihistamines. Serlopiant was well tolerated and safe in doses up to 5mg daily, and there were no treatment related serious adverse events. Based on this data, we have chosen to compare 5mg serlopiant vs. placebo. When assessing pruritus with a visual analog scale (VAS), symptoms were reduced in a statistically significant manner in both the 1mg ($p = 0.001$) and the 5mg ($p = 0.002$) dose groups when compared to placebo. After 6 weeks of treatment, nearly 70% of participants taking 5mg of serlopiant reported a 2-point reduction in VAS while nearly 50% of participants reported a 4-point decrease in VAS.

In a Phase 2 dose-ranging study of 557 subjects examining treatment of overactive bladder, the most common clinical AEs across all treatment groups were headache (5.7%), diarrhea (5.2%), urinary tract infection (4.7%), dry mouth (4.5%), nasopharyngitis (4.5%), upper respiratory tract infection (4.3%), fatigue (4.1%), dizziness (3.8%), back pain (2.9%), nausea (2.3%), and peripheral edema (2.2%).

Serlopitant has been more recently evaluated in a Phase 2 study of 257 adult subjects 18-65 years of age with chronic pruritus (TCP-101). In this study, treatment-emergent AEs (TEAEs) were reported in 25.4% of subjects in the placebo group and in 31.3%, 36.9%, and 37.5% of subjects in the serlopitant 0.25 mg, 1 mg, and 5 mg groups, respectively. Two severe TEAEs were reported: hypothyroidism in one subject in the serlopitant 0.25 mg group and peripheral neuropathy in one subject in the serlopitant 5 mg group. Both of these events were considered not related to study treatment.

Treatment-related TEAEs were reported in 7.9% of TCP-101 subjects in the placebo group and in 10.9%, 13.8%, and 12.5% of subjects in the serlopitant 0.25 mg, 1 mg, and 5 mg groups, respectively. “Nervous systems disorders” was the SOC with the highest incidence of treatment-related adverse events.

One SAE (spontaneous abortion) occurred in a TCP-101 subject in the serlopitant 1 mg group. This event was considered not related to study treatment. Five subjects (three in the placebo group, one in the serlopitant 1 mg group, and one in the serlopitant 5 mg group) discontinued the study as a result of a TEAE. Two of these subjects had events considered not related to study treatment (pruritus in 2 subjects) and three subjects had events considered to be treatment related (headache in one subject; diarrhea in one subject; and symptoms of a panic attack in one subject).

There was no evidence of meaningful trends in laboratory abnormalities or changes in vital signs in the TCP-101 study. Two subjects had a clinically significant change in an electrocardiogram (ECG): 1 subject in the serlopitant 0.25 mg group changed from normal to abnormal (clinically significant), and 1 subject in the serlopitant 5 mg group shifted from abnormal (not clinically significant) to abnormal (clinically significant).

Overall, the nonclinical and clinical studies to date have demonstrated that serlopitant has an acceptable safety and pharmacokinetic profile, and they support the further evaluation of Serlopitant in pruritus-related indications.

Overall, headache was the most commonly reported TEAE in TCP-101, reported in 6.3% of subjects in the placebo group and in 1.6%, 4.6%, and 1.6% of subjects in the serlopitant 0.25 mg, 1 mg, and 5 mg groups, respectively. Somnolence and diarrhea were the TEAEs with the highest overall incidence in the active-treatment groups. Somnolence was reported in 1.6% of subjects in the placebo group and in 1.6%, 4.6%, and 4.7% of subjects in the Serlopitant 0.25 mg, 1 mg, and 5 mg groups, respectively. Diarrhea occurred in 1.6% of subjects in the placebo group and in 0%, 6.2%, and 3.1% of subjects in the serlopitant 0.25 mg, 1 mg, and 5 mg groups, respectively. Most of the TCP-101 TEAEs were mild or moderate in severity.

Overall, the nonclinical and clinical studies to date have demonstrated that serlopitant has an acceptable safety and pharmacokinetic profile, and had been supported for further evaluation of Serlopitant in pruritus-related indications. Moreover, existing nonclinical data in adult animals and cumulative clinical data in adults support clinical trials in adolescents.

7) Preliminary unpublished data:

There is a trend towards greater reduction in itch severity as measured by daily self-reported NRS itch severity for serlopitant 5 mg as compared to placebo during the two month active trial period, though this was not statistically significant.

8) Experimental design and data analysis:

Inclusion criteria:

1. Males or females who are at least 13 years of age.
2. Willing and able to understand and sign informed assent/consent. Adolescents will need a parent or guardian willing and able to give consent.
3. Clinical diagnosis of epidermolysis bullosa (DEB, EBS, or JEB).
4. Subjects must have pruritus of at least 6 weeks duration
5. History of chronic pruritus
6. On the Stanford EB Itch survey, subject must have a Screening Visit (Visit 1) NRS pruritus score of at least 4 on either (1) average itch score in the past 24 hours or (2) bathing/dressing itch score in the past 24 hours.
7. Female subjects must be of non-childbearing potential (ie, post-menopausal for at least 1 year, had a hysterectomy, or had a tubal ligation) or, if of childbearing potential, must have a confirmed negative urine pregnancy test prior to study treatment and be willing to use effective contraception for the duration of the trial. Effective contraception is defined as follows: oral/implant/injectable/ transdermal contraceptives, intrauterine device, condom with spermicide, or diaphragm with spermicide. Abstinence or partner's vasectomy is acceptable if the female agrees to use effective contraception if she decides to discontinue abstinence or to have sexual intercourse with a non-vasectomized partner.
8. Judged to be in good health based upon the results of a physical examination, medical history, and safety laboratory tests.

Exclusion criteria:

1. Have any medical condition or disability that would interfere with the assessment of safety or efficacy in this trial or would compromise the ability of the subject to travel to Stanford or to undergo study procedures or to give informed consent.
2. Have a history of sensitivity to any components of the study material.
3. Are females of childbearing potential who are unwilling to use adequate contraception or who are breast feeding.
4. Have any chronic or acute medical condition that, in the opinion of the investigator, might interfere with the study results or place the subject at undue risk.
5. Have chronic renal disease, ie, serum creatinine greater than 2 times the upper limit of normal.
6. Have chronic liver disease, ie, AST or ALT greater than 2 times the upper limit of normal. Subjects with hepatitis B and C who have normal liver function may be enrolled.
7. Have a current malignancy (such as Hodgkin's lymphoma, B or T cell lymphoma, or myeloma) or blood cell dyscrasia (eg, polycythemia or myelofibrosis) that would lead to systemic chronic pruritus.
8. Subjects with untreated hyperthyroidism.
9. Have pruritus of psychogenic etiology (delusions of parasitosis, obsessive compulsive disorder and major depression) or neuropathic etiology (due to shingles, spinal cord injury or with neurologic deficit).
10. Have pruritus due to urticaria, drug allergy, or infection (such as pityriasis rosea or tinea or active human immunodeficiency virus [HIV]). Note: Subjects with HIV who have undetectable viral load, CD 4 counts >200 cells/cc, and stable retroviral therapy may enroll.
11. Have taken investigational medications within 30 days prior to Screening.
12. Are unwilling to discontinue specific pruritus medications for at least two weeks prior to initiation of study and throughout the study period (all severe CYP34A inhibitors - this

- includes **miconazole**, **delavirdine**, conivaptan, Clarithromycin, telithromycin, nefazodone, itraconazole, ketoconazole, indinavir, lopinavir, nelfinavir, **ritonavir**, saquinavir).
13. Within in the past 12 months, have expressed suicidal ideation with some intent to act.
 14. Started or changed medications, creams, or emollients including over-the-counter (OTC) preparations or bath oil treatment for relief of pruritus within 3 months prior to Screening.
 15. Have any social or medical condition (e.g. alcoholism, drug dependency, psychotic state) that, in the investigator's opinion, might interfere with the subject's ability to comply with the requirements of the protocol.

Statistical basis for the number of subjects to be enrolled:

This 14 patient clinical trial is powered only to determine large differences in the placebo (N=7) vs. 5 mg (N=14) groups. In power calculations, we assumed a mean of 8 NRS for the placebo vs. 5 NRS for the active with a SD of 3, and p-value of 0.05 (one sided).

| Two-sample t test with equal variances | | | | | |
|--|-----|------------------------|-----------|-------------------------|----------------------|
| | Obs | Mean | Std. Err. | Std. Dev. | [95% Conf. Interval] |
| x | 14 | 5 | 0.8017837 | 3 | 3.267852 6.732148 |
| y | 7 | 8 | 1.133893 | 3 | 5.225463 10.77454 |
| combined | 21 | 6 | 0.7121396 | 3.263434 | 4.514503 7.485497 |
| diff | -3 | 1.38873 | | -5.906646 | -0.0933544 |
| Diff= mean (x) – mean (y) | | | | t = -2.1602 | |
| Ho: diff = 0 | | | | Degrees of freedom = 19 | |
| Ha: diff < 0 | | Ha: diff != 0 | | Ha: diff > 0 | |
| Pr(T < t) = 0.0219 | | Pr(T > t) = 0.0437 | | Pr(T > t) = 0.9781 | |

Statistical plan for analyzing at least the primary hypothesis:

The sample size is powered to detect small differences in NRS score. Because itch is subjective and varies daily, subjects will be asked to keep an itch diary every day. For each subject, we will plot their average itch scores over time before and after drug intervention. For each dosage group, we will use linear regression methods with mix effects (GLM, SAS) to track the change in itch in each of the groups from baseline. This study will provide the effect size, standard deviation and range of itch scores in EB patients in order to properly power a larger phase 2 trial. This study can detect large differences in itch scores should Serlopitant decrease itch from severe to low-none at 1 and 2 months. At the 3 month follow up, we will measure the durability and length of response.

Matrix showing procedure plan for each study visit:

| Schedule of Events for Phase 2 Serlopitant | | | | | | | |
|--|------------------|-----------------|------------------------------|----------------|----------------|----------------|----------------|
| | Screening period | | Treatment period | | | Follow up | |
| | Phone call | Visit 1 | | Visit 2 | Visit 3 | Phone call | Early Term |
| | Screening call | Screening visit | Determination of Eligibility | Month 1 | Month 2/EOT | Month 3 | |
| Examination | Day -60 to -30 | Day -44* to -1 | Months 6 to 0 | Day 30 ±14 | Day 60 ±14 | Day 90 ±14 | |
| Informed consent/ Photographic consent | | X | | | | | |
| Demographics | | X | | | | | |
| Medical history | | X | Review | | | | |
| Prior ^a & current medications | X | X | | X | X | X | X |
| Abbreviated physical examination | | X | | | X | | X |
| Vital signs | | X | | X | X | | X |
| Urine pregnancy test (UPT) ^b | | X | Review results | X | X | | X |
| Inclusion/exclusion criteria | X | X | | | | | |
| Blood samples for clinical laboratory tests ^c | | X ^c | Review results | X ^c | X ^c | | X ^c |
| Randomization | | | X ^h | | | | |
| NRS ^d & Stanford EB survey | | X | | X | X | X ^e | X |
| Photograph the affected area ^f | | X | | X | X | | X |
| Dispense study medication | | | X ^h | X | | | |
| Dispense subject diary | | X | X ^h | X | X ^g | | |
| Review/collect diary with subject | | | | X | X | X | X |
| Review and record adverse events | | | | X | X | X | X |

Note: NRS = numeric rating score.

* Includes up to 30 day washout from prohibited medications. The study medication and diary dispensation are to occur no more than 1-2 weeks after Screening Visit.

- a: all medications taken within 30 days prior to screening.
- b: for females of child-bearing potential.
- c: all subjects: hematology, serum chemistry will be measured at Screening, Month 1, and Month 2/EOT or early termination (ET).
- d: NRS recorded by subject daily, using diary, from screening visit through the end of the study; NRS is included in the Stanford EB Itch survey.
- e: the Stanford EB survey will be administered over the phone by a member of the research staff.
- f: photographs taken only if patient has signed photography consent
- g: a return envelope will be provided for the patient to return the study diary to Stanford after the follow up phone call

| | Schedule of Events for Phase 2 Serlopitant | | | | | | |
|--|--|---------|------------------|---------|---------|------------|------------|
| | Screening period | | Treatment period | | | Follow up | |
| | Phone call | Visit 1 | | Visit 2 | Visit 3 | Phone call | Early Term |

h: Patient letter of enrollment and study medication will be mailed to patient after determination of eligibility following the Screening Visit

Each subject will be un-blinded individually after completing 3 months of study period. All patients who complete the study will be offered a 2-month trial on active drug. Patient who received active drug in the first phase will be contacted and asked if they would like to continue on active drug for an additional 2 months. Patients who received placebo in the first phase will be contacted and asked if they would like to repeat the study on open label for 2 months.

When this occurs, the schedule of events will be as follows:

Patients who would like to continue with the treatment for the open-label extension portion of the study will be provided with the research medication and research daily diary. They will be followed up by phone at baseline, 1 month, 2 months, and 3 months (wash out). In addition, they will go to an external lab near their home for lab monitoring that will occur once a month for the two months they are on active drug.

Data Monitoring Plan:

The Principal Investigator will provide oversight on monitoring safety/AEs/SAEs at this site. While there is not Data Safety Monitoring Board, the PI will act as the medical expert who answers safety/medical questions and who will provide medical expert opinion on this study. All AEs will be regularly reviewed and evaluated. The investigator will assess whether the AE represents an unanticipated problem (UP). If the investigator determines that the AE represents a UP, the investigator will promptly report the AE to the IRB. If the adverse event does not qualify as a UP, the adverse event should be reported at continuing review.

FDA Reporting:

In this study, the occurrence of any SAE from the time of informed consent until 4 weeks after the last dose of study drug will be reported to the Stanford IRB and the FDA within 24 hours of coming to the attention of the investigator.

Reporting any unexpected fatal or life-threatening suspected adverse reactions to the FDA will occur no later than 7 calendar days after initial receipt of the information.

Reporting any serious, unexpected suspected adverse reactions, findings from other clinical, animal or in-vitro studies that suggest significant human risk, and (3) a clinically important increase in the rate of a serious suspected adverse reaction to the FDA and all investigators will occur no later than 15 calendar days after determining that the information qualifies for reporting.

Submission of annual progress reports will occur within 60 days of the anniversary of the date that the IND went into effect (date that clinical studies were permitted to begin).

9) Significance:

Management of chronic pruritus is notoriously challenging for patients with EB. In a comprehensive survey of 146 EB patients, itch was reported as the most bothersome EB symptom, ranking higher than acute or chronic pain or problems eating.¹ Furthermore, pruritus can induce an itch-scratch-blister cycle, which can exacerbate existing wounds or induce new wounds.² There have been no new drugs for chronic pruritus, and the current management of pruritus in EB with anti-histamines and topical steroids only minimally relieve itch.³

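### The diary NRS is the implied primary measure, but the plan names no primary time point, itch item or drug-versus-placebo contrast

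*Combined protocol and SAP*

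**What the plan says.** **Aims (section 5).** Itch is to be assessed by self-report, using a "numeric rating scale (NRS) for itch severity and the Stanford EB itch questionnaire". Only the wound objective is given a rank: "A secondary aim of this study is to determine whether Serlopiant when compared with placebo reduces EB wounds".

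**Sample size (section 8).** The calculation uses the NRS alone: "we assumed a mean of 8 NRS for the placebo vs. 5 NRS for the active with a SD of 3". The level is one-sided 0.05. No time point is attached.

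**Statistical plan (section 8).** The heading refers to a primary hypothesis, but the text states none. It describes a daily itch diary and a mixed-effects regression that follows change from baseline within each dosage group. It adds that the study could detect a large effect "should Serlopitant decrease itch from severe to low-none at 1 and 2 months". Month 3 has a separate role: "At the 3 month follow up, we will measure the durability and length of response". The Stanford questionnaire is given no analysis.

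**Which NRS.** Footnote d to the Schedule of Events has the NRS recorded daily in the diary and also says "NRS is included in the Stanford EB Itch survey". Inclusion criterion 6 shows two itch scores, one for average itch and one for bathing or dressing. No section says which one the diary records or which is the endpoint.

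**The concern.** Two things are left open. First, the aim is a comparison with placebo, but the analysis text describes only trends within each group. Two within-group changes, one significant and one not, do not show that the arms differ. With 7 placebo subjects, a non-significant placebo trend would be unremarkable whatever the drug does.

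Second, nothing fixes which result answers the question. Month 1 or Month 2, average itch or bathing itch, diary or survey, NRS or questionnaire could each be put forward once the data are known. Arm codes are opened subject by subject after three months, so the choice need not be made blind.

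At stake are the meaning of any p-value and the effect estimate that this study is meant to pass to a larger phase 2 trial. Picking the better of several results biases that estimate upward.

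**Working it through.** **1. The plan's own figure.** Inputs from the sample-size section: 14 active, 7 placebo, means 5 and 8, SD 3.

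- SE = 3 × √(1/14 + 1/7) = 1.38873
- t = (5 − 8) / 1.38873 = −2.1602 on 14 + 7 − 2 = 19 degrees of freedom
- one-sided p = 0.0219, two-sided p = 0.0437

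This matches the printed output. It is a t test on assumed means, for a single NRS comparison; no power is stated. From the noncentral t distribution, the power it implies is 66.9% at one-sided 0.05. (The text says "This 14 patient clinical trial is powered only to determine large differences in the placebo (N=7) vs. 5 mg (N=14) groups", but the arms add to 21. That is a separate inconsistency; I follow the printed table.)

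**2. False-positive rate if any one of k results could count as success.** If the results were independent, the rate is 1 − 0.95^k:

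- k = 2 (NRS at two months): 1 − 0.95² = 9.75%
- k = 4 (two instruments × two months): 1 − 0.95⁴ = 18.5%

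The results cannot be independent: they come from the same subjects, and the survey contains the NRS. The documents give no correlations, so I assume a range. The rates below come from 200,000 simulated null trials of 14 versus 7, using one-sided pooled t tests at 0.05 and a common correlation.

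| Assumed correlation | NRS, two months | Two instruments × two months |
|---|---|---|
| 0.5 | 8.9% | 14.6% |
| 0.7 | 8.1% | 12.3% |
| 0.9 | 6.9% | 8.9% |
| 1 | 5.0% | 5.0% |

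**3. Bias in the estimate.** Suppose the true effect is the same at both months and the larger NRS difference is reported. The average overstatement is SE × √((1 − ρ)/π), where ρ is the correlation between the two monthly differences:

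- ρ = 0.9: 1.389 × √(0.1/3.1416) = 0.25 points
- ρ = 0.7: 1.389 × √(0.3/3.1416) = 0.43 points

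The assumed true difference is 3 points.

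**4. Naming one primary against splitting alpha.** Power for a 3-point difference, SD 3, 14 versus 7:

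- one test at 0.05: 66.9%
- Bonferroni for two (0.025): 53.6%
- Bonferroni for four (0.0125): 41.2%

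One named primary keeps the error rate at 5% without this loss.

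**The case against.** The strongest reply is that the plan does choose an instrument. The sizing and the text under the primary-hypothesis heading use the NRS alone, so the two instruments do not in practice have equal standing. That stands, and it makes the two-month NRS figures the more relevant ones.

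A reader might go further and infer that four tests are planned and that the one-sided 5% level is therefore broken. The documents do not support this. The analysis described is a longitudinal model; the mention of 1 and 2 months comes in a remark about what the study could detect; and no rule says that any one favourable result is enough. The 5% itself appears only as a sizing assumption. Counting every survey item and score to reach a still larger number of tests has even less support: the bathing/dressing item appears only as an entry criterion, and no questionnaire score is defined.

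Nor do the documents show that no comparison with placebo is intended. The aims and the two-sample sizing both point to one, and a mixed model could supply it through a group-by-time term. The gap is that the term, the time and the test are not written down.

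Finally, the study is partly exploratory, meant to supply an effect size and SD for a larger trial. That weakens the case for strict family-wise control. It does not remove the need for a named primary, because selection distorts the effect size itself.

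Section 7 reports a non-significant trend in daily NRS for 5 mg against placebo over two months. The description resembles this trial, but the source is not stated, so it does not establish that outcome data from this trial have been examined.

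**Conclusion.** The concern holds in limited form. It is certain that no primary time point, NRS item, diary summary or between-arm contrast is declared, and that the questionnaire is unranked beside the NRS. Followed as written, the plan yields within-group trends and leaves the deciding result open.

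The size is conditional. If either NRS month could count, the error rate is about 7% to 8% instead of 5%, at assumed correlations of 0.9 to 0.7, with 9.75% under independence. If either instrument at either month could count, it is about 9% to 12%, with 18.5% as an upper bound. These figures rest on an unwritten any-one-wins reading and on correlations that the documents do not give. This should be corrected before analysis; it does not invalidate the design.

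**What to change.** State one primary analysis: the between-arm difference in mean diary NRS, for one stated itch item, over a pre-specified on-treatment window, adjusted for the mean of the last 7 diary days before first dose, and tested once at one-sided 0.05.

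A suitable window is the last 7 diary days on study drug up to the Month 2/EOT visit, with days counted from first dose. A fixed calendar window would be less safe. The visit is allowed at Day 60 ± 14, that is Day 46 to Day 74, so if dosing ends at the visit, a window such as Days 54 to 60 could fall entirely off drug. Because medication is mailed, the plan should also say how the first-dose date is recorded.

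Report Month 1 NRS and the Stanford questionnaire as secondary, either in a fixed testing order or as estimates with confidence intervals and no claim. If any outcome data have already been seen, the amendment should say so.

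The cost is a few lines; the diary already runs daily from the screening visit. The downside is small: Month 1 and questionnaire results become supportive only.

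### Entry on bathing/dressing itch alone leaves average itch with no minimum, and the planned change-from-baseline analysis states no adjustment for the differing starting levels

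*Combined protocol and SAP*

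**What the plan says.** - **Entry.** Inclusion criterion 6 (section 8) asks for a screening NRS of "at least 4 on either (1) average itch score in the past 24 hours or (2) bathing/dressing itch score in the past 24 hours". Either item is enough. Criteria 4 and 5 concern duration and history of pruritus, so no other criterion sets a severity minimum.
- **Outcome.** Section 5 names "patient self-reports using a numeric rating scale (NRS) for itch severity and the Stanford EB itch questionnaire". Note d to the Schedule of Events has "NRS recorded by subject daily, using diary, from screening visit through the end of the study" and adds that "NRS is included in the Stanford EB Itch survey". Neither place says which item the diary asks or which is analysed.
- **Analysis.** The statistical plan says "For each subject, we will plot their average itch scores over time before and after drug intervention", then specifies linear regression with mixed effects "to track the change in itch in each of the groups from baseline". It lists no covariates and does not define baseline.
- **Sizing.** The statistical basis for the number of subjects states "we assumed a mean of 8 NRS for the placebo vs. 5 NRS for the active with a SD of 3", for 14 active and 7 placebo subjects. The same paragraph gives the trial total as 14, which does not match 14 + 7 = 21, so both sizes are carried below.

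**The concern.** A subject with troublesome itch at bathing or dressing but little itch otherwise is eligible. On average itch, that subject may start near the bottom of the scale beside others who start high. Three things follow for an analysis of change.

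1. Room to improve depends on where the subject starts (floor effect).
2. Subjects who start high tend to fall, and those who start low tend to rise, whatever the treatment (regression to the mean).
3. In arms this small, randomisation will often leave the arms with different mean starting levels.

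Subtracting baseline does not remove the second and third together. It corrects for the baseline difference with a slope of 1, when the right slope is usually smaller. The result is a noisier comparison and, in any one realised allocation, a shift favouring the arm that happened to start higher. The study is also meant to supply the effect size and SD for a larger trial, so the noise would carry forward.

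**Working it through.** **1. The plan's own figure.** Inputs from the sizing paragraph and table: means 5 and 8, SD 3, n = 14 and 7.

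- SE = 3 × √(1/14 + 1/7) = 1.3887
- t = (5 − 8)/1.3887 = −2.160 on 19 df, one-sided p = 0.0219

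This reproduces the table. The 3 points is a difference between arm means. The implied power at one-sided 0.05 (noncentral t) is 66.9% for 14 v 7 and 54.7% for 7 v 7, so there is little precision to spare.

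**2. How easily the arms can differ at baseline.** Two illustrations, both on assumed inputs.

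- *Count.* Suppose 7 of 21 subjects have low average itch, allocated 14:7. Let X be the number of these in the placebo arm; X is hypergeometric. The difference in low-baseline share is X/7 − (7−X)/14 = (3X−7)/14. It is at least 28 percentage points in absolute value unless X is 2 or 3. P(X=2) = 42042/116280 = 0.362 and P(X=3) = 35035/116280 = 0.301, so the chance of such an imbalance is 1 − 0.663 = 0.337, about 34%.
- *Mean.* If the baseline SD is also 3 (assumed), the chance difference in mean baseline has SE 3 × √(1/14 + 1/7) = 1.39 points for 14 v 7, and 3 × √(2/7) = 1.60 points for 7 v 7.

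**3. What that does to a change score.** With equal baseline and follow-up variances and correlation rho, a baseline difference of D shifts the change-score comparison by (1 − rho) × D in favour of the arm that started higher. At an assumed rho of 0.5, a one-SE imbalance shifts it by 0.5 × 1.39 = 0.69 points (14 v 7) or 0.5 × 1.60 = 0.80 points (7 v 7). Averaged over all randomisations the shift is zero; in one trial it is not.

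**4. Gain from adjusting.** Per-subject variance of change is 2σ²(1 − rho). Residual variance after regression on baseline is σ²(1 − rho²). The ratio is (1 + rho)/2. Estimating the slope costs, on average and for normal baselines, a factor 1 + 1/(N − 4): 18/17 = 1.059 for N = 21 and 11/10 = 1.10 for N = 14.

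| rho (assumed) | change, ÷σ² | adjusted, ÷σ² | ratio | net, N = 21 | net, N = 14 |
|---|---|---|---|---|---|
| 0.3 | 1.40 | 0.91 | 0.65 | 0.69 | 0.72 |
| 0.5 | 1.00 | 0.75 | 0.75 | 0.79 | 0.83 |
| 0.7 | 0.60 | 0.51 | 0.85 | 0.90 | 0.94 |

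The net gain vanishes only when (1 + rho)/2 times the slope factor reaches 1. That is rho = 2 × 17/18 − 1 = 0.89 for N = 21, and 2 × 10/11 − 1 = 0.82 for N = 14.

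**The case against.** **The sizing is not contradicted.** A reader might infer that anyone entering with average itch below 3 defeats the plan because that person cannot fall by 3 points. The documents do not support this. The sizing requires no fall in any individual. Low-baseline subjects can pull the mean difference down, but they are not inconsistent with it. An SD of 3 around 8 also already allows some low scores: under a normal distribution about 4.8% lie below 3.

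**No power loss can be quoted.** A reader might also want to say how much power the either/or rule costs. The share of subjects entering on bathing/dressing alone, and their average itch, appear nowhere in the documents. Any illustration also tends to alter the plan's own mean. With one third of subjects at 2 and the rest at 8, the arm mean is 2/3 + 16/3 = 6, not 8. To keep a mean of 8, the rest would have to average (8 − 2/3)/(2/3) = 11, which is off a 0 to 10 scale (range assumed; the documents do not state it). Such figures would test whether a mean of 8 is plausible, not criterion 6 itself. This objection stands in full.

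**Change from baseline, or a subject random effect, may already handle starting level.** In part. Change removes the baseline difference with a slope of 1, which over-corrects whenever rho is below 1 (step 3). A mixed model that treats baseline as a response with a common mean across arms would achieve much the same as adjustment, but the plan does not say that it does this. The text is brief, so the absence of a covariate may be an omission rather than a decision. It is still what the plan states.

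**The outcome may be the average item after all.** The phrase "we will plot their average itch scores over time before and after drug intervention" could mean that item, or a mean of diary scores on an unnamed item. On the first reading, bathing-only entrants have no minimum on the outcome. On the second, the outcome is not tied to either qualifying score. In both cases starting level on the outcome is unrestricted for some subjects.

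**Conclusion.** The point holds as one about efficiency and chance imbalance. The entry rule leaves average itch without a minimum, the outcome item is not fixed, and the stated analysis of change has no baseline adjustment. At an assumed rho of 0.3 to 0.7, adjustment would cut the variance of the treatment comparison by about 10% to 31% with 21 subjects, or 6% to 28% with 14, net of estimating the slope. It would also remove most of a chance shift that could plausibly be 0.7 to 0.8 points at rho 0.5.

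These sizes rest on assumed values of rho, equal variances, a baseline SD of 3 and roughly normal baselines. Restricted or floor-bound scores would change them somewhat. Any dilution of the effect by low-baseline entrants is possible but cannot be sized from the documents. Adjustment reduces noise and chance imbalance; it does not restore a diluted effect. It is worth changing, but it does not undermine the design.

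**What to change.** - Leave criterion 6 as it is.
- Name 24-hour average itch, from the diary, as the analysed item for every subject, whichever item qualified them. Report bathing/dressing itch separately as a secondary item.
- Define baseline as each subject's mean on that item over the diary days before first dose, not the screening score used for eligibility, which is selected to be high for those who qualified on it. Include it as a covariate in a mixed model that compares the arms.
- Confirm that pre-treatment diary days will exist. The schedule marks diary dispensing at Visit 1 and again when medication is mailed, while its starred note places diary dispensing with the medication after screening. State a fallback, such as the average item on the screening survey, for subjects with no diary days before dosing.
- An analysis restricted to subjects with baseline average itch of at least 4 is optional. Drawn from 14 or 21 subjects, it would be very imprecise and should be labelled as such.

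The cost is analysis wording and one degree of freedom (19 to 18 with 21 subjects, 12 to 11 with 14, in the simple two-arm comparison). Note d already provides for daily scores from screening, and recruitment is unaffected.
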